5.1.2 Planned number of subjects and sites

A total of approximately 300 subjects are planned to be randomized.

Stratification of subjects by age category is planned to ensure that an appropriate number of subjects will be included in each age range. The age categories are as follows:

- At least 100 subjects ≥ 4 years to < 12 years of age
- At least 100 subjects ≥ 12 years to < 17 years of age

Approximately 149 sites are planned in order to recruit the required subjects; additional sites will be added if deemed necessary.

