7.10 Randomization and numbering of subjects

An IXRS will be used for assigning eligible subjects to a treatment regimen based on a predetermined randomization schedule provided by UCB BIOSCIENCES. The randomization schedule will be produced by a UCB BIOSCIENCES biostatistician who is otherwise not involved in this study. The IXRS is responsible for issuing subject kits of study medication, as appropriate, according to the visit schedule.

To enroll a subject (Visit 1), the investigator will contact the IXRS and provide brief details about the subject to be enrolled. Each subject will receive a 5-digit number assigned at Screening which serves as the subject identifier throughout the study. The subject number will be required in all communication between the investigator (or designee) and the IXRS regarding a particular subject. Subject numbers and kit numbers will be tracked via the IXRS.

To randomize a subject (Visit 2), the investigator (or designee) will contact the IXRS and provide brief details about the subject to be randomized. The IXRS will allocate kit numbers to the subject based on the subject number during the course of the study.

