13.3 Planned efficacy analyses

13.3.1 Analysis of the primary efficacy variable

The assessment of efficacy is based on seizure frequency.

The primary efficacy variable is the change in partial-onset seizure frequency per 28 days from Baseline to the Maintenance Period.

Seizure frequency per 28 days will be calculated as $(\text{[number of seizures over the specified time interval]} / \text{[number of days in the interval]}) \times 28$. For subjects who prematurely discontinue the study, last observation carried forward method will be applied to obtain a seizure frequency estimate for the Maintenance Period.

Seizure frequency will be analyzed using analysis of covariance (ANCOVA) with terms for treatment and center (properly pooled), on log-transformed seizure frequency using the transformation of $\ln(X+1)$, where X is the seizure frequency. Log transformed baseline seizure frequency will be used as a covariate. The seizure frequency between treatment and placebo will be compared using least squares means (LSMs). The percent reduction over placebo will be estimated as $100 \times (1 - \exp[\text{LSM LCM} - \text{LSM placebo}])$.

It is planned to properly pool centers by geographic location. The final strategy for pooling will be determined prior to the unblinding of the study.

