13.3.2 Analysis of secondary efficacy variables

The secondary efficacy variables for this study are described in Section 4.1.2.

Subjects will be categorized as responders if the reduction in partial-onset seizure frequency from the Baseline Period to the appropriate treatment period meets the level specified in the given analysis. Response to treatment will be summarized for the proportion of subjects experiencing a $\geq 25\%$ to $< 50\%$, 50 to 75% , or $> 75\%$ reduction in partial-onset seizure frequency from the Baseline Period to the Maintenance Period. Proportion of subjects experiencing no change in partial-onset seizure frequency (ie, between $< 25\%$ reduction and $< 25\%$ increase in seizure frequency) and the proportion of subjects experiencing $\geq 25\%$

increase in partial-onset seizure frequency from the Baseline Period to the Maintenance Period will be presented. These response categories will also be presented from Baseline to the Treatment Period.

The difference in responder rate for 50% reduction in partial-onset seizure frequency between the LCM treatment group and placebo will be analyzed using a logistic regression model with effects for treatment and pooled center. No other statistical testing will be performed for the other secondary variables related to reduction in partial-onset seizure frequency.

The number and percentage of subjects experiencing a <50%, 50 to 75%, or >75% reduction in seizure frequency from Baseline to each post-Baseline visit will be presented by treatment group. The descriptive statistics for percent change in seizure frequency per 28 days from Baseline to each post-Baseline visit, the Maintenance Period, and entire Treatment and Maintenance Periods will be presented by seizure type and treatment group. No inferential testing will be performed for these summaries.

The change in seizure frequency per 28 days from Baseline to the Treatment Period, defined as the combined Titration and Maintenance Periods, will be summarized by treatment group (LCM or placebo) using descriptive statistics. Statistical testing will be performed using an ANCOVA model with terms for treatment and pooled center and Baseline seizure frequency as a covariate.

The change in seizure frequency by period will also be summarized using descriptive statistics by treatment group and seizure type.

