## **4 STATISTICAL/ANALYTICAL ISSUES**

### **4.1 Adjustments for covariates**

An analysis of the primary efficacy variable and analyses of several other efficacy variables will be adjusted for Baseline seizure frequency and pooled center.

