### **8.1.2 Primary analysis of the primary efficacy variable**

Seizure frequency will be analyzed using analysis of covariance (ANCOVA) with terms for treatment and center (pooled appropriately), on log-transformed seizure frequency using the transformation of  $\ln(X+1)$ , where X is the seizure frequency. Log transformed Baseline seizure frequency will be used as a covariate. Assumptions for the parametric model will be evaluated by diagnostic (eg, Shapiro-Wilk test for normality) and graphical methods such as residual plots, including normal probability plots, histograms, and plots of residuals versus Baseline covariate values and treatment. An assessment will be made with regards to the influence of individual observations (eg, extreme outliers) on the analysis. To the extent feasible, such potential influential observations will be identified prior to unblinding, and an assessment will be made with regard to the potential impact of such data, including the evaluation of alternative statistical methodology such as non-parametric methods. If deemed that a non-parametric method is warranted, an ANCOVA model on rank of seizure frequency per 28 days with terms for treatment and center (pooled appropriately) will be employed as the primary analysis. Ranked seizure frequency per 28 days during the Baseline Period will be used as a covariate.

The seizure frequency between treatment and placebo will be compared using the least squares means (LSMs). The percent reduction over placebo will be estimated as  $100 \times (1 - \exp[\text{LSM}_{\text{LCM}} - \text{LSM}_{\text{placebo}}])$ . A 95% CI will also be calculated for the percent reduction over placebo.

Partial-onset seizure frequency per 28 days during the Baseline Period and during the Maintenance Period, and the change from Baseline will be summarized by treatment group. This summary will be repeated by treatment group and age group, using the levels defined in section 4.8.

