### **8.2.2 Proportion of responders, where a responder is a subject experiencing a 50% or greater reduction in partial-onset seizure frequency from Baseline to end of Maintenance Period**

The secondary efficacy variable is the proportion of responders, where a responder is a subject experiencing a 50% or greater reduction in partial-onset seizure frequency from Baseline to the end of Maintenance Period.

Percent reduction will be calculated as  $([\text{absolute reduction in partial-onset seizure frequency}] \div [\text{Baseline partial-onset seizure frequency}]) \times 100$ .

Absolute reduction in partial-onset seizure frequency is calculated as  $(\text{Baseline partial-onset seizure frequency}) - (\text{Maintenance Period partial-onset seizure frequency})$ .

The subject is considered a responder if the data shows a 50% or greater reduction in partial-onset seizure frequency from Baseline to end of Maintenance Period, otherwise the subject will be considered a non-responder.

This variable will be analyzed using a logistic regression model with terms for treatment and center to measure the association between the response variable and treatment after controlling for center. The odds ratio, 95% CI, and p-value associated with treatment will be presented.

The number and percentage of responders will be summarized by treatment group.

The response to treatment for each response level will also be summarized using descriptive statistics by treatment group and seizure type, with the seizure types presented as follows: simple partial seizures (IA), complex partial seizures (IB), partial seizures evolving to secondarily generalized (IC), generalized seizures (II), and unclassified epileptic seizures (III). This summary will be repeated by treatment group and age group, using the levels defined in section 4.8.

Only subjects who experienced the respective seizure type during the Baseline Period will be included in the analysis for that seizure type with only the seizure frequencies of that seizure type being used in the analysis. Subjects can be analyzed under multiple seizure types in these summaries. No statistical testing will be performed for these by seizure type summaries.

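### Stratification by age category is planned, but age is in no efficacy model and the documents do not say whether it is a randomization stratum or an enrolment quota (minor)

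*Protocol*

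**What the plan says.** **Age in the design.** Protocol 5.1.2, on planned numbers of subjects and sites, says: "Stratification of subjects by age category is planned to ensure that an appropriate number of subjects will be included in each age range". It then sets a minimum of 100 subjects in each of two categories (4 to under 12 years, 12 to under 17 years) out of about 300. SAP 2.3 repeats this.

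**Age in the randomization.** Protocol 7.10 says: "An IXRS will be used for assigning eligible subjects to a treatment regimen based on a predetermined randomization schedule". It names no stratification factor. Nor do Protocol 5.1 (1:1 allocation) and 7.9 (blinding and the IXRS).

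**Age in the models.**
- Primary ANCOVA, Protocol 13.3.1: "Seizure frequency will be analyzed using analysis of covariance (ANCOVA) with terms for treatment and center (properly pooled), on log-transformed seizure frequency", with log Baseline frequency as covariate. SAP 8.1.2 matches: "with terms for treatment and center (pooled appropriately), on log-transformed seizure frequency".
- Rank fallback in SAP 8.1.2, which may become the primary analysis: "an ANCOVA model on rank of seizure frequency per 28 days with terms for treatment and center (pooled appropriately"), with ranked Baseline frequency as covariate.
- Treatment Period ANCOVA (Protocol 13.3.2, SAP 8.2.1): treatment, pooled center or site, and Baseline frequency.
- 50% responder model: "will be analyzed using a logistic regression model with effects for treatment and pooled center" (Protocol 13.3.2) and "This variable will be analyzed using a logistic regression model with terms for treatment and center" (SAP 8.2.2).
- SAP 4.1, where covariates are declared: efficacy analyses "will be adjusted for Baseline seizure frequency and pooled center".

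Age category is used only for subgroup and descriptive summaries (SAP 4.8, 8.1.2, 8.2.1, 8.2.2). SAP 3.9 reports no changes to the protocol-defined analyses.

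**The concern.** A factor used to stratify randomization normally goes into the analysis model. Balancing allocation on a prognostic factor reduces the true variance of the treatment estimate. A model without that factor leaves its variance in the error term, so the reported standard error is larger than the true one. The test is then conservative and some power is given up.

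If age only governs enrolment, nothing is mismatched. It is still a known baseline factor, and prespecifying it would remove some residual variance and correct for chance imbalance between arms.

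What is at stake is a little precision on the primary and responder comparisons, and an ambiguity that is easy to close before unblinding and awkward to close afterwards.

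**Working it through.** **Inputs.** Protocol 13.8 and SAP 2.4 give a log-scale difference of 0.249, SD 0.73, 135 per arm, two-sided 5%, 80% power, and responder rates of 22% (placebo) and 40% (LCM). Allocation is 1:1 (Protocol 5.1). The documents do not say how strongly age predicts outcome. R², the share of residual variance explained by age category, is therefore an assumption shown as a range.

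**The plan's own figures.** d = 0.249/0.73 = 0.341 (printed as 0.342). n = 2(1.960 + 0.842)²/d² = 134.9, so 135 per arm, as stated. The 87% responder power also reproduces with the continuity correction. Leaving age out does not alter the stated sample size. By noncentral t with 268 degrees of freedom, the noncentrality is 0.341 × √(135/2) = 2.802, the critical value is 1.969, and power is 79.7%. This is the base figure below.

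**If age is a randomization stratum** (allocation balanced within age category). The true variance of the estimate carries the factor 1 − R² whether or not age is modelled.
- Age included: noncentrality 2.802/√(1 − R²), critical value 1.969.
- Age omitted: same noncentrality, but the inflated standard error raises the effective critical value to 1.969/√(1 − R²).
- True alpha with age omitted (normal approximation): 2[1 − Φ(1.960/√(1 − R²))].

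| Assumed R² | True alpha, age omitted | Power, omitted | Power, included | Gain (points, unrounded inputs) |
|---|---|---|---|---|
| 1% | 0.049 | 79.9% | 80.1% | 0.3 |
| 2% | 0.048 | 80.0% | 80.5% | 0.6 |
| 5% | 0.044 | 80.3% | 81.7% | 1.4 |

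At R² = 10% alpha is 0.039. The normal approximation then gives power of 81.3% omitted against 84.0% included.

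**If age is only a quota** (allocation not balanced on age). The age-omitted analysis has its nominal power of 79.7%. With age included it is 80.1%, 80.5% or 81.7% at R² = 1%, 2% or 5%, a gain of 0.4, 0.8 or 2.0 points. The one degree of freedom spent does not change these figures as rounded.

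**Responder model.** Simulation: 136 per arm, two equal age strata, allocation balanced within strata, center effects ignored, 3,000 runs per scenario. The odds ratio was (0.40/0.60)/(0.22/0.78) = 2.36. Simulation error is about 0.4 points for type I error and 0.6 for power. The placebo rates by age category are assumed.

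| Placebo rates by age | Type I error, omitted / included | Power, omitted / included |
|---|---|---|
| 17% / 27% | 4.2% / 4.7% | 89.1% / 89.5% |
| 12% / 32% | 4.1% / 4.8% | 85.3% / 87.3% |

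The pattern is the same: slightly conservative, with a power difference that stands clear of simulation error only when age is strongly prognostic.

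**The case against.** The best case against acting is that Protocol 5.1.2 describes a quota. Its stated purpose is to secure numbers in each age range, it sits in the section on planned enrolment, and its two minimums leave about 100 of the 300 places free. No randomization passage names a stratum. A reader might infer from the word stratification that the analysis contradicts the design; the documents do not establish that. They do not rule it out either. Both documents use the word, medical history records an age group category (Table 5-1, footnote d), and SAP 6.1 can draw age from the system used to randomize. The ambiguity stands.

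A reader might also set 79.7% against 81.7% and take the 2.0 points as the price of ignoring a stratum. That mixes two scenarios. Under age-balanced allocation the age-omitted power at R² = 5% is already 80.3%, so the loss is 1.4 points. The larger gain belongs to unstratified allocation, where nothing is mismatched.

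Three further objections stand. Nothing shows that age explains any variance once Baseline frequency and country-pooled center are in the model; if R² is near zero, the gain is nil. Age is not ignored, since efficacy summaries are repeated by age group. And the change is more than an edit to the SAP, because the model terms are fixed in Protocol 13.3.1 and 13.3.2.

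**Conclusion.** The point holds as a minor one. Stratification by age category is planned, no efficacy model carries it, and neither document says whether age is a randomization stratum.

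If it is a stratum, and R² is 1% to 5%, the omission costs about 0.3 to 1.4 points of power and lowers true alpha to between 0.049 and 0.044. If it is a quota, there is no mismatch, and including age would gain about 0.4 to 2.0 points over the same range and correct chance imbalance. These figures rest on the assumed R² and, in the stratum case, on allocation balanced within age category.

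It would be wrong to conclude that the primary test is invalid. The omission causes no bias and no type I error inflation, and 135 per arm stands. The reason to act is that power is only 80%, the re-estimated sample size is capped at 149 per arm before the dropout adjustment (Protocol 13.7), and the factor is already collected.

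**What to change.** Before unblinding:

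1. State in Protocol 5.1.2 and 7.10, and in SAP 2.3, whether age category is a randomization stratum or an enrolment quota.
2. Add age category (4 to under 12, 12 to under 17 years) as a fixed factor to the SAP 8.1.2 ANCOVA and its rank fallback, the 8.2.1 ANCOVA and the 8.2.2 logistic model.
3. List it among the adjustments in SAP 4.1.
4. Record it in SAP 3.9 as a change from the protocol-defined models.

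The cost is one degree of freedom per model and a declared departure from the protocol's model terms. In the logistic model the treatment odds ratio also becomes conditional on age, so it estimates a slightly different quantity and should be labelled accordingly. No new data are needed and the planned sample size does not change.

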5.1.3 Anticipated regions and countries

The study will be conducted in the [REDACTED], and the [REDACTED] with the possibility to expand the study to other countries and regions if deemed necessary.

5.2 Schedule of study assessments

[Table 5-1](#), [Table 5-2](#), and [Table 5-3](#) present the tabular schedules of study procedures.

Table 5-1 Schedule of study assessments (Baseline Period, Titration Period, Maintenance Period, Early Termination Visit, and Unscheduled Visits)

Assessments	Baseline Period (8 weeks)			Treatment Period (16 weeks)											ET	Unscheduled Visit ^c
	VI ^a	T1	V2	Titration Period (6 weeks)						Maintenance Period (10 weeks)						
Visit	VI ^a	T1	V2	T2	V3	T3	V4	T4	V5	V6	T5	V7	T6	V8 ^b	ET	Unscheduled Visit ^c
Week in study	-8	-4	0	1	2	3	4	5	6	8	10	12	14	16		
Informed consent	X															
Inclusion/exclusion criteria	X	X	X													
Medical history ^d	X															
Seizure history	X															
Concomitant medications	X	X	X	X	X	X	X	X	X	X	X	X	X	X	X	X
Concomitant AEDs	X	X	X	X	X	X	X	X	X	X	X	X	X	X	X	X
VNS assessment ^e	X		X		X		X		X	X		X		X	X	X
Physical examination (complete)	X		X											X	X	
Physical examination (brief)					X		X		X	X		X				
Tanner Stage ^f	X													X	X	
Vital signs (BP and pulse rate, including orthostatic assessments)	X		X		X		X		X	X		X		X	X	X
Body weight ^g	X		X ^g		X		X		X	X		X		X	X	X
Height	X		X											X	X	
Head circumference	X													X	X	
Neurological examination (complete)	X		X											X	X	
Neurological examination (brief)					X		X		X	X		X				
ECG (12-lead) ^h	X		X		X		X		X	X		X		X	X	

Table 5-1 Schedule of study assessments (Baseline Period, Titration Period, Maintenance Period, Early Termination Visit, and Unscheduled Visits)

Assessments	Baseline Period (8 weeks)			Treatment Period (16 weeks)											ET	Unscheduled Visit ^c
	VI ^a	T1	V2	Titration Period (6 weeks)						Maintenance Period (10 weeks)						
Visit	VI ^a	T1	V2	T2	V3	T3	V4	T4	V5	V6	T5	V7	T6	V8 ^b	ET	Unscheduled Visit ^c
Week in study	-8	-4	0	1	2	3	4	5	6	8	10	12	14	16		
Clinical chemistry/hematology	X		X				X		X			X		X	X	
Endocrinology			X											X	X	
Urinalysis ^d	X		X				X		X			X		X	X	
Serum pregnancy test ^e	X						X		X			X		X	X	
Urine pregnancy test ^f			X		X					X						
Concomitant AED plasma concentrations ^g	X								X					X	X	
LCM plasma concentration ^h	X								X					X	X	
C-SSRS ⁱ	X		X		X		X		X	X		X		X	X	X
Clinical Global Impression of Change														X	X	
Caregiver's Global Impression of Change														X	X	
Achenbach CBCL ^m			X						X					X	X	
BRIEF-P/BRIEF ⁿ			X											X	X	
PedsQL ^o			X											X	X	
Contact IXRS	X		X		X		X		X	X		X		X	X	
Randomization ^p			X													
Dispense study medication			X ^q		X		X		X	X		X		X	X	
Study medication return					X		X		X	X		X		X	X	
Subject diary ^r	X	X	X	X	X	X	X	X	X	X	X	X	X	X	X	X
Withdrawal criteria		X	X	X	X	X	X	X	X	X	X	X	X	X		X

Table 5-1 Schedule of study assessments (Baseline Period, Titration Period, Maintenance Period, Early Termination Visit, and Unscheduled Visits)

Assessments	Baseline Period (8 weeks)			Treatment Period (16 weeks)											ET	Unscheduled Visit ^c
				Titration Period (6 weeks)						Maintenance Period (10 weeks)						
Visit	V1 ^a	T1	V2	T2	V3	T3	V4	T4	V5	V6	T5	V7	T6	V8 ^b		
Week in study	-8	-4	0	1	2	3	4	5	6	8	10	12	14	16		
AE reporting	X	X	X	X	X	X	X	X	X	X	X	X	X	X	X	X
Assessments of epilepsy surgery/VNS	X															
Health care resource use	X		X		X		X		X	X		X		X	X	

AE=adverse event; AED=antiepileptic drug; BP=blood pressure; BRIEF=Behavior Rating Inventory of Executive Function; BRIEF-P=Behavior Rating Inventory of Executive Function-Preschool Version; CBCL=Child Behavior Checklist; C-SSRS=Columbia-Suicide Severity Rating Scale; ECG=electrocardiogram; ET=Early Termination Visit; IXRS=interactive voice/web response system; LCM=lacosamide; PedsQL=Pediatric Quality of Life Inventory; T=Telephone Contact; V=Visit; VNS=vagus nerve stimulation

Note: For all visits shown in Table 5-1, a time window of ± 2 days relative to Visit 2 (Baseline Period) is applicable. During the Treatment Period, each visit should occur at the end of the week indicated in accordance with this time window.

^a Visit 1 (V1) may occur over more than 1 day; however, all results of Baseline/Visit 1 assessments should be available before randomization on Visit 2.

^b At the end of Visit 8, subjects who complete the Maintenance Period may be eligible to participate in an open-label extension study (EP0034). Subjects who plan to enroll in the open-label extension study will proceed to a 4-week blinded Transition Period. Subjects who choose not to enter the open-label extension study or who do not complete the Maintenance Period will proceed to a blinded Taper Period (2 to 4 weeks, depending on dose level achieved). Taper of LCM may not be required for some subjects who discontinue study medication prematurely, depending on the treatment option selected by the investigator in consultation with the subject and/or parent/legal representative.

^c If an Unscheduled Visit is needed (eg, due to AE), then the assessments noted will be performed. Additional assessments may be performed at the investigator's discretion. The C-SSRS will be completed at an Unscheduled Visit only if the visit is related to an AE.

^d Medical history to include demographics (date of birth [where permitted], age group category, age in months and years, race, ethnicity, and gender).

^e Only applicable for subjects with an implanted VNS device.

^f The Tanner Stage will be performed only for subjects who are pubescent at Visit 1 or who enter puberty during the course of the study.

^g The subject's body weight at Baseline (Visit 2) will be used to determine dose throughout the study.

^h A 12-lead ECG (2 interpretable recordings) will be performed prior to any blood draws and vital signs assessment. The subject should rest in the supine position for approximately 5 minutes before the recordings and during the recordings, if possible. The recordings should be made 20 to 30 minutes apart.

ⁱ Urinalysis will be performed for subjects ≥ 5 years of age only.

- ^j Pregnancy tests will be performed for female subjects of childbearing potential only.
- ^k Blood samples for analysis of concomitant AED plasma concentrations and/or LCM will be drawn along with clinical chemistry, hematology, and endocrinology samples, as applicable.
- ^l The C-SSRS will be completed for all subjects ≥ 6 years of age. The C-SSRS will be completed at an Unscheduled Visit only if the visit related to an AE.
- ^m The Achenbach CBCL: CBCL/1½ -5 for children 18 months to 5 years and 11 months of age, and CBCL/6-18 for children ≥ 6 years to < 17 years of age at Screening; to be completed by the parent(s)/legal representative(s) (estimated completion time 45 minutes). For each subject, the same version of the scale that was completed at Visit 2 (CBCL/1½ -5 or CBCL/6-18) should be maintained for the duration of the study and should be completed by the same parent/legal representative. The Achenbach CBCL will be used only in countries where a translated version is available.
- ⁿ The BRIEF-P should be used for subjects who are ≥ 2 years to < 5 years of age at Visit 2, and the BRIEF should be used for subjects who are ≥ 5 years of age at Visit 2. The same version of the scale that was completed at Visit 2 (BRIEF-P or BRIEF) should be maintained for each subject for the duration of the study. The BRIEF-P and BRIEF will be used only in countries where a translated version is available.
- ^o The version of the PedsQL used at Visit 2 should be consistent with the subject's age at Visit 2 and should be maintained for each subject for the duration of the study. The PedsQL will be used only in countries where a translated version is available.
- ^p At the end of Visit 2, subjects should take the first dose of study medication in the clinic.
- ^q The subject diary will be dispensed at Visit 1. At all subsequent visits, the subject and/or legal representative(s) will be reminded to complete the diary on a daily basis.

Table 5-2 Schedule of study assessments (Transition Period)

Assessment	Transition Period (4 weeks) ^a			
	TV1	TV2	TV3	TV4
Visit				
Week in study	17 ^a	18	19	20
Concomitant medications	X	X	X	X
Concomitant AEDs	X	X	X	X
VNS assessments ^b	X	X	X	X
Physical examination (complete)				X
Physical examination (brief)	X	X	X	
Vital signs (BP and pulse rate, including orthostatic assessment)	X	X	X	X
Body weight	X	X	X	X
Neurological examination (complete)				X
Neurological examination (brief)	X	X	X	
12-lead ECG ^c				X
Clinical chemistry/hematology				X
Urinalysis ^d				X
Urine pregnancy test ^e				X
Concomitant AED plasma ^f concentrations				X
LCM plasma concentration ^f				X
C-SSRS ^g	X	X	X	X
Contact IXRS	X	X	X	X
Dispense study medication	X	X	X	
Study medication return	X	X	X	X
Subject diary ^h	X	X	X	X
Withdrawal criteria	X	X	X	X
AE reporting	X	X	X	X
Health care resource use	X	X	X	X

AE=adverse event; AED=antiepileptic drug; BP=blood pressure; C-SSRS=Columbia-Suicide Severity Rating Scale; ECG=electrocardiogram; IXRS=interactive voice/web response system; LCM=lacosamide; TV=Transition Visit; VNS=vagus nerve stimulation

Note: For all visits shown in Table 5-2, a window of ± 2 days relative to Visit 2 (Baseline Period) is applicable. Each visit should occur at the end of the week indicated in accordance with this time window.

^a At the end of Visit 8, (Maintenance Period), subjects may be eligible to participate in an open-label extension study (EP0034). Subjects who plan to enroll in the open-label extension study will enter a 4-week blinded Transition Period.

^b Only applicable for subjects with an implanted VNS device.

^c A 12-lead ECG (2 interpretable recordings) will be performed prior to any blood draws and vital signs

Table 5-2 Schedule of study assessments (Transition Period)

Assessment	Transition Period (4 weeks) ^a			
	TV1	TV2	TV3	TV4
Visit				
Week in study	17 ^a	18	19	20

assessment. The subject should rest in the supine position for approximately 5 minutes before the ECG recording and during the recordings if possible. The recordings should be made 20 to 30 minutes apart.

^d Urinalysis will be performed for subjects ≥ 5 years of age only.

^e Pregnancy tests will be performed for female subjects of childbearing potential only.

^f Blood samples for analysis of concomitant AED plasma concentrations and/or LCM will be drawn along with clinical chemistry, hematology, and endocrinology samples, as applicable.

^g The C-SSRS will be completed for all subjects ≥ 6 years of age.

^h The subject diary will be returned at TV4. At all other visits, the subject and/or legal representative(s) will be reminded to complete the diary on a daily basis.

Table 5-3 Schedule of study assessments (Taper Period and Safety Follow-Up Period)

Assessment	Taper Period ^a (2 to 4 weeks)		Safety Follow-Up Period ^b (30 days)	
	TV ^c	Taper Visit ^d	Safety Follow-Up Visit	Safety Follow-Up Telephone Contact
Week in study	17	18, 19, or 20	20, 21, or 22	22, 23, or 24
Concomitant medications	X	X	X	X
Concomitant AEDs	X	X	X	X
VNS assessment ^e		X	X	
Physical examination (brief)		X		
Physical examination (complete)			X	
Vital signs (BP and pulse rate, including orthostatic assessment)		X	X	
Body weight		X	X	
Neurological examination (brief)		X		
Neurological examination (complete)			X	
ECG (12-lead) ^f		X	X ^g	
Clinical chemistry/hematology		X	X ^g	
Endocrinology		X	X ^g	
Urinalysis ^h		X	X	
Serum pregnancy test		X	X ⁱ	

Table 5-3 Schedule of study assessments (Taper Period and Safety Follow-Up Period)

Assessment	Taper Period ^a (2 to 4 weeks)		Safety Follow-Up Period ^b (30 days)	
	Visit	Taper Visit ^d	Safety Follow-Up Visit	Safety Follow-Up Telephone Contact
Week in study	T7 ^c	18, 19, or 20	20, 21, or 22	22, 23, or 24
Urine pregnancy test			X ⁱ	
C-SSRS ^j		X	X	
Contact IXRS		X		
Study medication return		X		
Subject diary ^k	X	X		
Withdrawal criteria	X	X		
AE reporting	X	X	X	X
Health care resource use		X	X	

AE=adverse event; AED=antiepileptic drug; BP=blood pressure; C-SSRS=Columbia-Suicide Severity Rating Scale; ECG=electrocardiogram; IXRS=interactive voice/web response system; LCM=lacosamide; T=Telephone Contact; VNS=vagus nerve stimulation

Note: The study week numbers provided are for subjects who complete the Maintenance Period and enter the Taper Period. The study week numbers provided do not apply to subjects who enter the Taper Period at other times.

^a A blinded Taper Period (2 to 4 weeks, depending on dose achieved) will be required for subjects who discontinue study medication prematurely and for subjects who complete the Maintenance Period but choose not to enter the open-label extension study (EP0034). Taper of LCM may not be required for some subjects who discontinue study medication prematurely, depending on the treatment option selected by the investigator in consultation with the subject and or parent/legal representative.

^b The Safety Follow-Up Visit will occur 2 weeks (± 2 days) after the final dose of study medication. The Safety Follow-Up Telephone Contact will occur 30 days ($-1/+3$ days) after the final dose of study medication.

^c A telephone contact (T7) will be conducted at the end of the first week of the Taper Period.

^d Each subject will have only 1 Taper Visit. The Taper Visit will be scheduled at the end of the Taper Period (Week 18, Week 19, or Week 20, depending on dose level achieved; see Table 7-5). A time window of ± 2 days relative to Visit 2 (Baseline Period) is applicable.

^e Only applicable for subjects with an implanted VNS device.

^f A 12-lead ECG (2 interpretable recordings) will be performed prior to any blood draws and vital signs assessment. The subject should rest in the supine position for approximately 5 minutes before the recording and during the recordings, if possible. The recordings should be made 20 to 30 minutes apart.

^g The assessment will only be required for subjects with an abnormal value (clinical chemistry, hematology, or endocrinology) or reading (ECG) at the previous clinic visit.

^h Urinalysis will be performed for subjects ≥ 5 years of age only.

ⁱ Pregnancy tests will be performed for female subjects of childbearing potential only. A serum pregnancy test will be performed at the Safety Follow-Up Visit only if blood is collected for other laboratory tests. If no blood is collected for other assessments, then a urine pregnancy test will be performed.

^j The C-SSRS will be completed for all subjects ≥ 6 years of age.

Table 5-3 Schedule of study assessments (Taper Period and Safety Follow-Up Period)

	Taper Period ^a (2 to 4 weeks)		Safety Follow-Up Period ^b (30 days)	
Assessment				
Visit	T7 ^c	Taper Visit ^d	Safety Follow-Up Visit	Safety Follow-Up Telephone Contact
Week in study	17	18, 19, or 20	20, 21, or 22	22, 23, or 24

^x At T7, the subject and/or legal representative(s) will be reminded to complete the diary on a daily basis. The subject diary will be returned at the Taper Visit.

